#### **6.1.3.2 Graphical presentation of results**

Individual time profiles and Mean (SD) plots of absolute and change from period baseline of percent of predicted FEV1 and all spirometry parameters will be presented by treatment group and time.

The results of statistical analysis will also be presented in a graphical representation showing the estimated mean differences to placebo and their confidence intervals per time point.

Corporate Confidential Information

## **6.2 Secondary objectives**

### **6.2.1 Variables**

parameters to be analyzed are all spirometry and LCI parameters and CFQ-R PRO questionnaire.

### **6.2.2 Descriptive analyses**

Absolute and change from baseline for all spirometry and LCI parameters will be listed by cohort, treatment, patient and visit/time and summarized by treatment group and dose level.

Summary statistics of these endpoints will be performed, split by the stratification of LCI results based on baseline FEV1 > 80% of predicted.

### **6.2.3 Statistical model, assumptions and hypotheses**

The primary model described for percent of predicted FEV1 in Section 6.1.3 will be used for all secondary parameters of interest (separate model for each parameter) for cohort 3. Treatment contrasts and their 80% two-sided confidence intervals will be derived at Day 7, Day 14, Day 21 and Day 28.

### **6.2.3.1 Graphical presentation of results**

Individual time profiles and Mean (SD) plots of absolute and change from baseline for all spirometry and LCI parameters will be presented by treatment group and dose level.

Correlation of change from baseline at each timepoint between spirometry and LCI endpoints will be presented.

Corporate Confidential Information

### **6.2.5 Lung volumes and small airway measurements**

Lung Volume parameters include:

- FRC, RV/TLC, difference between SVC and FVC

Small airway measurements parameters include:

- FEV3, 1-FEV3, FEV6, FEV3/FVC, 1-FEV3/FVC, FEV3/FEV6, 1-FEV3/FEV6, FEV1/FEV6 (assessed by spirometry)

Parameters obtained from spirometry and Pulse oximetry at each time-point and changes from baseline will be summarized by treatment group. In cohort 3 summary stats will be provided by time within period.

## **7 Statistical methods for safety and tolerability data**

### **7.1 Variables**

Adverse events, vital signs (blood pressure, pulse rate, body temperature), ECG intervals, laboratory measurements, as well as subject demographics, baseline characteristics, and treatment information.

### **7.2 Descriptive analyses**

#### **Subject demographics and other baseline characteristics**

All data for background and demographic variables will be listed by treatment group (treatment sequence for cohort 3) and subject. Summary statistics will be provided by treatment in cohorts 1 and 2 and overall (by sequence) in cohort 3.

Relevant medical history, current medical conditions, results of laboratory screens, drug tests and any other relevant information will be listed by treatment group (treatment sequence for cohort 3) and subject.

#### **Treatment**

Data for study drug administration (rescue medication) and concomitant therapies will be listed by treatment group (treatment sequence for cohort 3) and subject.

#### **Vital signs**

All vital signs data will be listed by cohort, treatment group (treatment sequence for cohort 3), subject, and visit/time and if ranges are available abnormalities (and relevant orthostatic changes) will be flagged. Summary statistics will be provided by treatment group and visit/time. In cohort 3 summary stats will be provided by time within period (Days 1,7,14,21,28)

#### **ECG evaluations**

All ECG data will be listed by cohort, treatment group (treatment sequence for cohort 3), subject and visit/time, abnormalities will be flagged. Summary statistics will be provided by treatment group and visit/time. In cohort 3 summary stats will be provided by time within period (Days -1,14,28)

#### **Clinical laboratory evaluations**

All laboratory data will be listed by cohort, treatment group (treatment sequence for cohort 3), subject, and visit/time and if normal ranges are available abnormalities will be flagged. A separate listing is provided presenting all parameters in a subject with any abnormal values. Summary statistics will be provided by treatment group and visit/time. In cohort 3 summary stats will be provided by time within period (Days -1,14,28)

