and slowing the decline in lung function (Hirsh 2002). This “rehydration” approach has been tested clinically in CF using inhaled amiloride, a direct blocker of the epithelial sodium channel (ENaC). Inhaled amiloride produced an enhancement of mucociliary clearance (App et al 1990), and initial promising reports regarding improvement in lung function (Knowles et al 1990); however with a prohibitively short duration of action in the airways and an estimated elimination half-life of around 23 minutes (Hofmann et al 1997) this compound lacked any robust clinical benefit (Pons et al 2000). Inhaled hypertonic saline, which increases ASL volume *in vitro* (Donaldson et al 2006), has been demonstrated to accelerate muco-ciliary clearance (MCC), reduce the frequency of pulmonary exacerbations, and improve lung function in CF (Elkins et al 2006 and Donaldson et al 2006) an early indication that an enhancement of MCC will be of clinical benefit in the disease. Unfortunately, hypertonic saline is often poorly tolerated in the clinic due to cough and bronchospasm, and thus there is a need for novel therapies targeting ENaC in the airway (Donaldson and Boucher 2007).

A potential consequence of an inhaled ENaC inhibitor is systemic exposure resulting in ENaC inhibition in the kidney. ENaC inhibition in the kidney can lead to hyperkalemia, hyponatremia, volume depletion, and a compensatory increase in aldosterone.

Corporate Confidential Information

On this basis, QBW276 represents a novel therapy with a potential for being disease-modifying in CF while avoiding the potential complications of hyperkalemia, hyponatremia, volume disturbance, and compensatory aldosterone elevation.

Corporate Confidential Information

Novartis

Confidential

Page 25

Amended Protocol Version v04 (Clean)

Protocol No. CQBW276X2201

Corporate Confidential Information

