EPOCH	SCREENING		TREATMENT PERIOD 1								TREATMENT PERIOD 2					
	Screening	Baseline	Day 1	Day 7	Day 14	Day 21	Day 28	Washout	Baseline/ET/EOS ²	Day 57	Day 63	Day 70	Day 77	Day 84	ET/EOS	
Visit Name	Screening	Baseline	Day 1	Day 7	Day 14	Day 21	Day 28	Washout	Baseline/ET/EOS ²	Day 57	Day 63	Day 70	Day 77	Day 84	ET/EOS	
Visit Numbers ¹	1	2	101	103	104	105	106	TC	199	201	202	203	204	205	299	
Study Day(s)	-45 to -14	-7 to -4	1	7 -2 +2	14 -2 +2	21 -2 +2	28 -2 [contact] -0 +2	57	63 -2 +2	70 -2 +2	77 -2 +2	84 -2 +0	91 -3 +3	
Informed consent	X															
Inclusion / Exclusion criteria	X	X							X ¹²							
Metabolite Screening Assay	X															
Corporate Confidential Information	X															
Randomization			X ¹⁰													
Contact IRT	X	X	X	X	X	X	X			X	X	X	X	X		
Study drug dispensation and administration in clinic in the morning			X	X	X	X	X			X	X	X	X	X		
Medical history/current medical conditions	X	X							X							
Concomitant therapies									X							
Demography	X															
Vital Signs	X	X	X ⁴	X ⁴	X ⁴	X ⁴	X ⁴		X	X ⁴	X ⁴	X ⁴	X ⁴	X ⁴	X	
Body height	X															
Body weight	X	X			X ⁴		X ⁴		X			X ⁴		X ⁴	X	
Physical examination	X	X			X ⁴		X ⁴		X			X ⁴		X ⁴	X	

EPOCH	SCREENING		TREATMENT PERIOD 1								TREATMENT PERIOD 2					
	Visit Name	Screening	Baseline	Day 1	Day 7	Day 14	Day 21	Day 28	Washout	Baseline/ET/EOS ²	Day 57	Day 63	Day 70	Day 77	Day 84	ET/EOS
Visit Numbers ¹	1	2	101	103	104	105	106		199	201	202	203	204	205	299	
Study Day(s)	-45 to -14	-7 to -4	1	7 -2 +2	14 -2 +2	21 -2 +2	28 -2 [contact] -0 +2	57	63 -2 +2	70 -2 +2	77 -2 +2	84 -2 +0	91 -3 +3	
Spirometry	X	X		X ⁴	X ⁴	X ⁴	X ⁴		X		X ⁴	X ⁴	X ⁴	X ⁴	X	
ECG evaluation	X	X			X ⁴		X ⁴		X			X ⁴		X ⁴	X	
Corporate Confidential Information			X			X		X				X			X	X
			X	X ⁴	X ⁴	X ⁴	X ⁴		X	X ⁴	X ⁴	X ⁴	X ⁴	X ⁴	X	
			X	X ⁴	X ⁴	X ⁴	X ⁴		X ¹³	X ⁹	X ⁹	X ⁹	X ⁹	X ⁹	X	
PK blood collection			X ⁹	X ⁹	X ⁹	X ⁹	X ⁹									
Central Lab Blood Chemistry ⁶	X	X	X ⁴	X ⁴	X ⁴	X ⁴	X ⁴		X	X ⁴	X ⁴	X ⁴	X ⁴	X ⁴	X	
Central Lab Hematology	X	X			X ⁴		X ⁴		X			X ⁴		X ⁴	X	
Hepatitis screen	X															
Corporate Confidential			X													
			X													
Alcohol Test, Drug Screen, and Cotinine Test	X	X								X						X
HIV screen	X															
Pregnancy test	X ⁷	X ⁸			X ^{4,8}		X ^{4,8}		X ⁸			X ^{4,8}		X ^{4,8}	X ⁸	
Urinalysis	X	X	X ⁴	X ⁴	X ⁴	X ⁴	X ⁴		X	X ⁴	X ⁴	X ⁴	X ⁴	X ⁴	X	
Telephone follow-up								X ³								
AEs and SAEs								X								

EPOCH	SCREENING		TREATMENT PERIOD 1								TREATMENT PERIOD 2					

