8.4.4 Laboratory evaluations

Clinically significant deviations of laboratory test results occurring at screening or baseline visits, or during or at completion of the study must be repeated, reported and/or discussed with Novartis personnel. The results should be evaluated for criteria defining an adverse event and reported as such if the criteria are met. Repeated evaluations are mandatory until normalization of the result(s) or until the change is no longer clinically relevant. In case of doubt, Novartis personnel should again be contacted.

Hematology

Hemoglobin, hematocrit, red blood cell count, white blood cell count with differential and platelet count will be measured.

Clinical chemistry

Sodium, potassium, bicarbonate, creatinine, blood urea nitrogen, uric acid, chloride, albumin, calcium, alkaline phosphatase, total bilirubin, LDH, GGT, AST, ALT, PT/INR, amylase, lipase CK, glucose, total cholesterol, triglycerides. If the total bilirubin concentration is increased above 1.5 times the upper limit of normal, direct and indirect reacting bilirubin should be differentiated.

Local blood chemistry (Cohorts 1 &2 only)

Sodium, potassium, chloride, bicarbonate collection to monitor for hyperkalemia.

Urinalysis

Routine urinalysis and Sodium/potassium ratio measurement will be provided by the central lab

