11.5.2 Safety

Vital signs

All vital signs data will be listed by cohort, treatment (treatment sequence for cohort 3), patient, and visit/time and if ranges are available abnormalities (and relevant orthostatic changes) will be flagged. Summary statistics will be provided by treatment and visit/time.

ECG evaluations

All ECG data will be listed by cohort, treatment (treatment sequence for cohort 3), patient and visit/time, abnormalities will be flagged. Summary statistics will be provided by treatment and visit/time.

Clinical laboratory evaluations

All laboratory data will be listed by cohort, treatment (treatment sequence for cohort 3), patient, and visit/time and if normal ranges are available abnormalities will be flagged. Summary statistics will be provided by treatment and visit/time.

Adverse events

For cohort 3, all information obtained on adverse events will be displayed by cohort, treatment sequence and patient.

The number and percentage of patients with adverse events will be tabulated by body system and preferred term with a breakdown by treatment. An adverse event starting in one period and continuing into the next period is counted only in the onset period. A patient with multiple adverse events within a body system and treatment period is only counted once towards the total of this body system and treatment.

Corporate Confidential Information

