### 1.2 Study reference documentation

This SAP has been developed using Clinical Trial Protocol version v02 dated 20-Mar-2017.

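### The single day list for cohort 3 laboratory summaries (SAP 7.2) fits hematology but leaves Day 7 and Day 21 chemistry and urinalysis out of the tables

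*SAP*

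**What the plan says.** SAP 7.2, under Clinical laboratory evaluations, covers all laboratory data in one paragraph. It first asks for summaries by treatment group and visit, then adds for cohort 3: "In cohort 3 summary stats will be provided by time within period (Days -1,14,28". It does not separate hematology, chemistry and urinalysis. The ECG paragraph of SAP 7.2 has the same cohort 3 list. The vital signs paragraph has a different one: "In cohort 3 summary stats will be provided by time within period (Days 1,7,14,21,28".

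The visits come from the cohort 3 part of Table 8-1 in protocol Section 8. There the row "Central Lab Blood Chemistry" is marked at baseline and on Days 1, 7, 14, 21 and 28 of each period, and urinalysis is marked at the same visits. The row "Central Lab Hematology" is marked at baseline and on Days 14 and 28 only.

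For laboratory data, protocol 11.5.2 says "Summary statistics will be provided by treatment and visit/time" and names no days. SAP 1.2 states: "This SAP has been developed using Clinical Trial Protocol version v02 dated 20-Mar-2017". The protocol supplied is v04.

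**The concern.** A list that suits one laboratory panel has been applied to all three. Read as written, it removes half of the on-treatment chemistry and urinalysis visits from the by-treatment tables, although the samples are taken and the protocol plans to summarise them.

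Protocol 2.2 names blood chemistry and urinalysis among the cohort 3 secondary safety endpoints. Protocol 1.1 describes hyperkalemia and hyponatremia as possible consequences of systemic exposure to an inhaled ENaC inhibitor, and presents QBW276 as a therapy with disease-modifying potential "while avoiding the potential complications of hyperkalemia, hyponatremia, volume disturbance, and compensatory aldosterone elevation". Protocol 8.4.4 limits the additional electrolyte testing: "Local blood chemistry (Cohorts 1 &2 only". In cohort 3, central chemistry is therefore the scheduled source of serum electrolytes, and it also carries creatinine and the liver tests. The tables are one place where these are compared between QBW276 and placebo, and their first on-treatment row would be Day 14.

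There may also be selection. Protocol 7.1 requires treatment to stop for certain laboratory abnormalities. A patient stopped on that ground after Day 7 and before Day 14 might contribute no on-treatment value to the tables. The documents give no basis for sizing this.

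**Working it through.** The plan states no figure here to reproduce. The check compares the SAP lists with the cohort 3 columns of Table 8-1.

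**Mapping.** Period 2 visits are numbered from study start. Subtracting 56 gives the day within period: 57, 63, 70, 77 and 84 become Days 1, 7, 14, 21 and 28. Day 1 samples are pre-dose, so Day 1 is not counted as on-treatment.

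**On-treatment visits per period**

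| Assessment | Scheduled (Table 8-1) | In the SAP list | Without a table |
|---|---|---|---|
| Chemistry | 7, 14, 21, 28 | 14, 28 | 2 of 4 |
| Urinalysis | 7, 14, 21, 28 | 14, 28 | 2 of 4 |
| Hematology | 14, 28 | 14, 28 | 0 of 2 |
| ECG | 14, 28 | 14, 28 | 0 of 2 |
| Vital signs | 7, 14, 21, 28 | 7, 14, 21, 28 | 0 of 4 |

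Over both periods, chemistry and urinalysis each lack 2 × 2 = 4 of 2 × 4 = 8 on-treatment visits (study Days 7, 21, 63 and 77), which is 50%. The pre-dose chemistry and urinalysis samples on Days 1 and 57 are also outside the list.

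**Volume.** For the 24 planned completers:

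- Scheduled on-treatment chemistry draws: 24 × 4 visits × 2 periods = 192.
- Draws outside the tables: 24 × 2 × 2 = 96, or 48 of 96 per treatment.

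The tables will use the safety set, so these counts are illustrative. The one-half share for a patient who completes both periods does not depend on the number of patients.

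**First on-treatment row.** It moves from Day 7 (7 ± 2, Days 5 to 9) to Day 14 (14 ± 2, Days 12 to 16).

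**Baseline label.** The list starts at Day -1. In Table 8-1 the cohort 3 Period 1 baseline visit is Day -7 to -4, so the label matches no scheduled Period 1 visit.

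**Comparison within the SAP.** Vital signs have the same Table 8-1 visits as chemistry and get all five treatment-period days. ECG has the hematology visits and gets the short list. The laboratory paragraph uses the ECG list, which suits only one of its three panels.

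**The case against.** The strongest reply is that the sentence just before the day list repeats the protocol's general rule, and that SAP 6.2.5 uses the same cohort 3 wording with no days at all. On that reading, the cohort 3 sentence only arranges output within period and the bracketed days are a loose illustration. This is possible but not the natural reading. The sentence names specific days, and the SAP names a different set for vital signs, so a programmer would follow the list. If all visits were intended, the text still needs correcting.

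The day lists are also abbreviated in general: the vital signs list omits the period baseline visits, and none of the three includes ET/EOS. That is true, and it weakens any claim that the lists mirror Table 8-1 exactly. It does not explain why on-treatment Days 7 and 21 are kept for vital signs and dropped for chemistry.

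Several limits on importance stand:

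- The SAP table of contents shows a Section 8.1 covering aldosterone, the urine sodium-to-potassium ratio and serum potassium. Its body is redacted, and those analytes may be summarised there on more days.
- All values remain in the listings with abnormal values flagged, and patients with abnormal values get a separate listing.
- SAP 7.3 plans laboratory boxplots without restricting days.
- Clinically significant values are reported as adverse events, and a DMC monitors safety.
- The trial is non-confirmatory, and the selection effect cannot be sized.

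Day -1 can be understood as a baseline label, and the mismatch may stem from the SAP having been written to v02. The v02 schedule is not available, so the origin cannot be established. Against the current protocol the mismatch exists.

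**Conclusion.** The SAP is wrong as written. In the SAP 7.2 tables for cohort 3, 2 of 4 on-treatment chemistry visits and 2 of 4 on-treatment urinalysis visits per period have no summary by treatment. This is narrower than protocol 11.5.2 and affects named secondary safety endpoints. Hematology loses no on-treatment visit.

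The conclusion rests on reading the cohort 3 day list as the operative instruction and on the v04 schedule. It applies only to the tables under SAP 7.2. It does not show that serum potassium or the urine sodium-to-potassium ratio goes unsummarised elsewhere. No data, listing, flag or statistical test is lost, so this should be corrected but is not critical.

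**What to change.** Replace the single cohort 3 sentence in SAP 7.2 with panel-specific days:

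- **Chemistry and urinalysis:** period baseline visit and Days 1 (pre-dose), 7, 14, 21 and 28 of each period.
- **Hematology:** period baseline visit and Days 14 and 28 of each period.

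Replace Day -1 with the period baseline visit, and check the SAP day lists against Table 8-1 of protocol v04. ET/EOS rows for each panel, and a summary of the worst on-treatment value, would be useful but are optional.

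The cost is one SAP sentence and a few more rows in tables already planned. No new data are needed. Making the change before database lock avoids choosing afterwards which safety visits to tabulate.

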## Adverse events

All information obtained on adverse events will be displayed by cohort, treatment group (treatment sequence for cohort 3) and subject.

The number and percentage of subjects with adverse events will be tabulated by body system and preferred term with a breakdown by treatment. A subject with multiple adverse events within a body system is only counted once towards the total of this body system and treatment.

For the legal requirements of ClinicalTrials.gov and EudraCT, two required tables on treatment emergent adverse events which are not serious adverse events with an incidence greater than 5% and on treatment emergent serious adverse events and SAE suspected to be related to study treatment will be provided by system organ class and preferred term on the safety set population.

If for a same patient, several consecutive AEs (irrespective of study treatment causality, seriousness and severity) occurred with the same SOC and PT:

- a single occurrence will be counted if there is  $\leq 1$  day gap between the end date of the preceding AE and the start date of the consecutive AE
- more than one occurrence will be counted if there is  $> 1$  day gap between the end date of the preceding AE and the start date of the consecutive AE.

For occurrence, the presence of at least one SAE / SAE suspected to be related to study treatment / non SAE has to be checked in a block e.g., among AE's in a  $\leq 1$  day gap block, if at least one SAE is occurring, then one occurrence is calculated for that SAE.

The number of deaths resulting from SAEs suspected to be related to study treatment and SAEs irrespective of study treatment relationship will be provided by SOC and PT.

### 7.3 Graphical presentation

Boxplots to visualize trends in longitudinal safety data (vitals, ECG, lab parameter) will be created.

Corporate Confidential Information

---

Corporate Confidential Information

